5 STUDY DESIGN

5.1 General Description of the Clinical Investigation (ICH E3; 9)

Clinical Phase: Pivotal

Sample Size: At least 160 participants will be randomized (1:1 ratio) into two groups to use either VR101 or the sham ring.

Study Population: Sexually active women who report experiencing lack of lubrication during intercourse, give consent to participate and meet all inclusion/exclusion criteria.

Study Type: Multi-center, double-blind, sham-controlled parallel group study (followed by optional open-label extension).

Study Products: VR101 devices and sham rings (see descriptions above)

Study Regimen: Participants will be randomly assigned to receive either VR101 or the sham ring. Participants will then use 4 devices consecutively for 7 days each, (28 days total). Participants will be allowed to use VR101 for 2 weeks following the double-blind study in an open-label extension.

5.1.1 Study Endpoints (ICH E9; 2.2.2)

- **Primary**: Proportion of participants that experience increased vaginal lubrication that enhances ease and comfort of intimate sexual activity, defined as an FSFI-LD \geq 4.5 with 4 consecutive weeks of weekly ring use.

J3 Bioscience, Inc.	Clinical Investigation Plan and Protocol CI03	CI03-CIP Rev. 02 Page 25 of 60
	A Clinical Investigation to Evaluate Efficacy of the J3 Bioscience Lubricating Intravaginal Ring VR101 as a Personal Lubricant Device in Women	

- **Exploratory:** Improvement in the Female Sexual Function Index (FSFI) total composite score (Rosen 2000) and its domains (Desire, Arousal, Lubrication, Orgasm, Satisfaction and Pain) during 28 days of use.
- **Safety endpoints monitored:**
 - Any adverse events and adverse device effects (ADE)

5.1.2 Measures to Minimize Bias

- Participants will not have access to their previous responses, and thus, in any given FSFI survey participants will be unable to directly reference their previous responses.
- All participants, regardless of randomization status, will be presented with the same study materials, including device packaging and labeling, will undergo the same measurements, and will be presented with the same survey questions.

5.1.3 Test Equipment, Maintenance, and Calibration

No test equipment is needed for evaluation of safety or efficacy of device use.

5.2 Exposure to VR101 and the Sham Ring

Participants will use VR101 for up to 42 (± 2) days or the sham ring for up to 28 (± 2) days.

5.3 Study Participants

5.3.1 Inclusion Criteria for Participant Selection (ICH E3; 9.3 ICH E9; 2.2.1)

Clinical Investigation Participants Must:

1. Completely understand and sign the informed consent form (ability to read and understand the consent form in the English language).
2. Be at least 21 years of age.
3. Express willingness to comply with the entire study visit schedule (see Table 7 in study procedures section).
4. Over the course of the study:
 - a. Abstain from the use of any vaginal moisturizers or lubricants or any other topically applied vaginal products not provided by study staff during the entirety of study participation
 - b. Abstain from using lubricated or spermicide-containing male or female condoms
 - c. Abstain from vaginal intercourse with a male partner using a lubricated condom

J3 Bioscience, Inc.	Clinical Investigation Plan and Protocol CI03	CI03-CIP Rev. 02 Page 26 of 60
	A Clinical Investigation to Evaluate Efficacy of the J3 Bioscience Lubricating Intravaginal Ring VR101 as a Personal Lubricant Device in Women	

- d. Abstain from any oral sex during or prior to vaginal intercourse with a male partner.
- e. Must not initiate, modify or discontinue a regimen of HRT (hormone replacement therapy) or estrogen-containing birth control.

NOTE: women who have been using non-vaginal HRT or estrogen-containing birth control (e.g., oral, transdermal) on a regular dosing interval continuously for at least 3 months may continue on the same regimen during the study

- f. Abstain from use of any other vaginally-placed devices (e.g. ring, diaphragm, cervical cap, pessary products)
 - g. If able to get pregnant, use an approved method of contraception (per remainder of I/E criteria) to reduce their risk of becoming pregnant during the study.
- 5. In the previous 3 months, have had or attempted sexual intercourse with a male partner a minimum of twice per month (on average).
 - 6. Respond to all 4 individual FSFI Lubrication Questions (7 - 10) with a score of 1, 2, or 3.
 - 7. Attempt sexual intercourse at least 4 times during the 4-week double-blind study.

5.3.2 Exclusion criteria for participant selection

Participants self-reporting any of the following will be ineligible for study entry:

- 1. Current use of HRT (Hormone Replacement Therapy) or any estrogen-containing birth control products, unless not applied vaginally and the participant has been on a regular dosing interval for at least 3 months prior and is willing to continue the same regimen without modification throughout study participation.
- 2. Vulvar or vaginal procedures (biopsies, radiation) in the last 3 months.
- 3. Active vulvar or vaginal infections/lesions or complaints, as well as undiagnosed abnormal genital bleeding.
- 4. History of chronic pelvic pain, interstitial cystitis, vulvar vestibulitis, pelvic inflammatory disease within the past 3 months.
- 5. Known current cervical or vaginal infection.
- 6. Participants who have given birth or terminated pregnancy in the past 6 weeks.
- 7. Postpartum or post-abortion endometritis, unless symptoms resolved at least 3 months prior to study entry.
- 8. Current persistent, abnormal vaginal bleeding.
- 9. History of inability to place a vaginal ring.
- 10. History of any abnormality of the vagina resulting in distortion of the vaginal canal or incompatibility with vaginal ring placement.

J3 Bioscience, Inc.	Clinical Investigation Plan and Protocol CI03	CI03-CIP Rev. 02 Page 27 of 60
	A Clinical Investigation to Evaluate Efficacy of the J3 Bioscience Lubricating Intravaginal Ring VR101 as a Personal Lubricant Device in Women	

11. Body habitus or history of lower genital tract abnormalities or prior surgeries, which may not allow the vagina to be appropriately accessed.
12. Known or suspected allergy or hypersensitivity to polyurethanes or glycerol.
13. Known current alcohol or illicit drug abuse.
14. Participants who have not recovered from adverse events due to chemotherapy or radiation treatment for cancer.
15. Uncontrolled intercurrent illness including, but not limited to, ongoing or active infection of the urogenital tract, symptomatic congestive heart failure, unstable angina pectoris, cardiac arrhythmia, or psychiatric illness/social situations that would limit compliance with study requirements.
16. Any condition that in the opinion of the investigator or study staff that would constitute contraindications to participation in the study or would compromise ability to comply with the study protocol.
17. Current use of a vaginally-placed device (e.g. ring, pessary, cervical cap or diaphragm) unless willingness to discontinue for the study duration is expressed.
18. Pregnancy or plans to become pregnant in the next 6 months.
19. Current breastfeeding.
20. Participation in a previous ViroPan or J3 Bioscience clinical trial for VR101 (i.e. CI01, CI02)

NOTE: IUD (Intrauterine Device) users may be enrolled provided they commit to exercising caution when removing VR101, as IUD strings have been noted to interfere with VR101 removal.

NOTE: Participants who have previously undergone anterior and/or posterior vaginal repair and have received a vaginal mesh implant may have difficulty placing VR101 but are not automatically excluded from the study.

5.3.3 Points of Enrollment

Participants will be considered to be enrolled upon providing consent, meeting all inclusion/exclusion criteria and signing the Informed Consent Form.

5.3.4 Duration of Participation

Participants will be enrolled in the study for a total of up to 49 days. The study will consist of a 28-day randomized trial where participants will use either VR101 or the sham ring followed by a 14-day open-label portion and a follow-up phone call 7 days after the open-label portion.

5.3.5 Randomization and Blinding

Each enrolled subject randomly assigned in a 1:1 ratio to receive either VR101 devices or sham rings. A randomization schedule (separate for each site) will be prepared for treatment group assignment of each subject. The subject's randomization number will be

J3 Bioscience, Inc.	Clinical Investigation Plan and Protocol CI03	CI03-CIP Rev. 02 Page 28 of 60
	A Clinical Investigation to Evaluate Efficacy of the J3 Bioscience Lubricating Intravaginal Ring VR101 as a Personal Lubricant Device in Women	

unique. This number is not the same as the subject identification (ID) number which is assigned at the time of informed consent.

The subject ID number identifies the subject and consists of the site number plus subject number for that site. The randomization number identifies the treatment; the randomization schedule provides the correspondence between the subject ID number and the randomized treatment identification (VR101 or sham).

The trial will be double-blind, meaning the subject and Investigator/staff will not have access to or knowledge of the subject's treatment assignment. Further, since the Sponsor will create and securely maintain the randomization schedules, the Sponsor and Sponsor's representatives will not be made aware of a given subject's randomization number until the blind is broken. The Sponsor will ensure that the Study Monitor does not ever have access to the randomization assignments.

As this is a multi-site study, the study coordinator will monitor enrollment to ensure nominally equal representation of the 160 subjects across the sites, for example if two sites are selected, at least 1/3 of participants (53) would be enrolled at each site. Additionally, the Sponsor will create and securely maintain a separate randomization schedule for each site to ensure appropriate site representation in the study groups.

5.3.6 Participant Withdrawal / Discontinuation

Participants may voluntarily withdraw from the investigation for any reason at any time. However, every effort will be made to schedule an Early Termination visit and collect final outcome measures as well as ascertain the reason for withdrawal.

Participants who withdraw from the study (or are removed by an investigator) due to an Adverse Event will be followed as described in Section 13.10.

Participants who begin a menstrual period during ring use should discontinue ring use and insert a new ring within 24 hours of cessation of menstruation. When a new ring is inserted, ring exchange will still occur on scheduled days (see Section 5.4.3). For example: If the new ring is inserted on day 6, 13, or 20, she will not need to change again on day 7, 14 or 21 (respectively) because leaving the ring in will still comply with the margin of error in the Visit Schedule.

Participants who become pregnant during the study will be instructed to discontinue use of study product and will be dropped from the study. Study staff will refer any such participants to a clinical facility for follow-up.

J3 Bioscience, Inc.	Clinical Investigation Plan and Protocol CI03	CI03-CIP Rev. 02 Page 29 of 60
	A Clinical Investigation to Evaluate Efficacy of the J3 Bioscience Lubricating Intravaginal Ring VR101 as a Personal Lubricant Device in Women	

5.3.7 Number of Participants

Enrollment will continue until at least 160 participants have been randomized into the study. For a 2-site study, at least 53 (~1/3 of total) participants must be enrolled at each study site.

5.3.8 Estimated Time Needed to Enroll Participants

Based on previous studies, we anticipate that enrollment of 160 participants can be completed in approximately 2 months.

5.3.9 Total Study Duration

The clinical investigation is expected to last approximately 3 to 4 months.

5.3.10 Procedures for the Replacement of Participants

Participants will not be replaced. Data from all randomized participants will be reviewed prior to data lock. Analysis groups and methods for dealing with any missing data will be assigned prior to unblinding for the primary and secondary efficacy analyses. Refer to the Draft Statistical Analysis Plan (SAP) for further details. The SAP for this study will be finalized and approved prior to final data analysis.

5.4 Procedures

5.4.1 Participant Screening

Participants will be screened according to study site procedures.

5.4.2 Participant Enrollment / Recruitment

- Interested women will be invited to learn more about this study. If an interested possible participant calls the study coordinator, the potential participant may be given information over the phone and emailed (or mailed) the informed consent form for review.
- The study information will be presented to potential participants and explained. Study Visit 1 will be scheduled if interest persists and the potential participant meets basic inclusion/exclusion criteria. Staff may email the informed consent form (ICF) to the potential investigation participant for review before her scheduled visit.
- A signed copy of the informed consent form (ICF) will be provided to the participant.
- The ICF will be stored with the participant's record or as part of the required investigation documentation.

J3 Bioscience, Inc.	Clinical Investigation Plan and Protocol CI03	CI03-CIP Rev. 02 Page 30 of 60
	A Clinical Investigation to Evaluate Efficacy of the J3 Bioscience Lubricating Intravaginal Ring VR101 as a Personal Lubricant Device in Women	

5.4.3 Visit Schedule and Description: Frequency and Timing of Study Variables (ICH E3; 9.5.1. ICH E9; 2.2.2)

Participants must return to the clinic for determination to return unused study product and take a final FSFI survey per the schedule shown in Table 7. At that time, all participants will be given the opportunity to use active VR101 rings for a 2-week period.

Table 7. Schedule of Events							
	Baseline	Treatment				Discontinuation/ Follow-Up	
Visit	1	PC	PC	PC	2	Early Term***	Final PC
Day (Nominal)	0	7±1	14±1	21±1	28±2	Study Withdrawal	49±2 (35±2)*
Informed Consent	X						
Assign Subject Number	X						
I/E Criteria	X						
Demographics	X						
Height & Weight	X						
Concomitant Therapy	X				X	X	
Pregnancy Test	X				X	X	
Administer Non- Lubricated Condoms (if needed)	X						
Brief Medical History	X						
FSFI Survey	X				X	X	
Intercourse / Lubricant Use Survey		X	X	X	X	X	
Dispensing of Randomized Product / Insertion of 1 st Ring in Clinic	X						
Removal of Final Randomized Ring / Dispensing of Open- Label Product Insertion of 1 st Ring in Clinic					X**		
Adverse Events	X	X	X	X	X	X	X
Ring Use Log	X	X	X	X	X	X	X**
Ring Change Reminder		X	X	X			
Returned Ring Collection					X	X	

*If a participant does not elect to participate in the open-label extension, the follow-up will occur on day 35±2 instead of day 49±2. **Only if the participant elects to participate in the open-label extension ***Only if a participant decides to withdraw participation before reaching Day 26
							

J3 Bioscience, Inc.	Clinical Investigation Plan and Protocol CI03	CI03-CIP Rev. 02 Page 32 of 60
	A Clinical Investigation to Evaluate Efficacy of the J3 Bioscience Lubricating Intravaginal Ring VR101 as a Personal Lubricant Device in Women	

Visit 1 – Study Start / Randomization (Day 0)

1. Assign a Subject Number to the prospective participant and complete initial screening procedures.
2. Participants will be administered the FSFI survey (see Section 5.4.6) by a trained member of the study staff. Complete this as early as possible in the Visit, e.g., as soon as consent is obtained.
3. A staff member will conduct a Concomitant Therapy assessment, during which they will assess and record if any hormonal therapies are currently being used or have been used in the past 3 months (these may or may not disqualify the participant from enrollment, refer to Inclusion / Exclusion Criteria above). During this assessment, women still able to get pregnant will be asked about their current birth control method. If the method is allowed by inclusion / exclusion criteria (see above), they will be instructed to continue their same method. If no birth control is currently used, or their preferred method is to use condoms, they will be offered non-lubricated condoms as to allow them to participate in the study.
4. As part of the demographic assessment, participants will be queried as to their menopausal status. If a prospective participant is still able to get pregnant, she will be asked to provide a urine sample for a pregnancy test.
5. If participant meets all inclusion and exclusion criteria, they will be enrolled and given a numbered package of randomized study product. All packages will be identical in appearance and will contain 6 individually packaged study devices (either VR101 or sham ring). All packages will contain a unique number, which will be recorded by study staff.
6. Enrolled participants will be shown to a private clinic area or restroom to self-insert one of the devices from the package. Participants will be asked to insert one of these rings per the instructions for use and without clinician input. If a participant has difficulty with placement, she can ask for further instruction or choose to not place the ring and will be withdrawn from the study (this will be recorded on an Early Termination CRF and reported to the Sponsor). If the ring was successfully placed, the participant will be instructed to leave the first ring in the vagina for 7 days.

NOTE: Used rings / packaging are not intended to be collected by study staff. However, the site Study Coordinator may consult the Sponsor to determine if used devices / packaging should be collected in case of any unusual patient reports / adverse events.

7. Study staff will record the date and time that the ring was successfully placed and note any assistance needed from study staff (e.g., physical, verbal) so that it can be recorded in the Ring Use Log (Section 5.4.8).
8. Participants will be instructed to exchange with a fresh ring on day 7, day 14 and day 21.

J3 Bioscience, Inc.	Clinical Investigation Plan and Protocol CI03	CI03-CIP Rev. 02 Page 33 of 60
	A Clinical Investigation to Evaluate Efficacy of the J3 Bioscience Lubricating Intravaginal Ring VR101 as a Personal Lubricant Device in Women	

NOTE: If the ring is expelled (unless on a normal exchange day), the participant will be asked to rinse it using tap water and reinsert unless it is not appropriate to reinsert the expelled ring (e.g., lost in toilet, soiled). If participant is unable or unwilling to reinsert the expelled ring, or if the ring has been out for more than 24 hours, she will be asked to store it, if possible, in a provided re-sealable bag and bring it to her next clinic visit. If this occurs:

- If expelled After the ring had been inserted for at least 6 days: she will be asked to start her next scheduled ring a day early.
- If the ring had only been inserted for 5 days or less: she will be asked to insert a new ring, which will be removed on the next scheduled day (e.g., day 7, 14, 21 or 28).

Visit 2 – Final visit, Treatment week 4 (Day 28 ± 2)

1. Participants will be asked to report any Adverse Events (AEs), and whether or not they feel the events were related to use of the investigational device. AEs will be recorded on the Adverse Event Form. Refer to Section 13 for further detail on classification of AEs and adverse device effects (ADEs).
2. If a participant is still able to get pregnant, she will be asked to provide a urine sample for a pregnancy test.
3. Participants will be administered the FSFI survey (see Section 5.4.6) by a trained member of the study staff.
4. A staff member will conduct a Concomitant Therapy assessment, during which they will determine the participant used any unapproved medication (e.g. change of dosing frequency of HRT / hormonal birth control).
5. Following the FSFI Survey, participants will be given the Intercourse / Lubricant Use Survey (see Section 5.4.7) to assess frequency of intercourse and assess if any unapproved lubrication sources were used.
6. Participants will be again queried as necessary to complete the Ring Use Log (see Section 5.4.8) up to all events that occur during Visit 2. If the participant does not continue in the open-label extension, then all information needed to fully complete all fields of her Ring Use Log should be collected during Visit 2.
7. Participants will be asked to return any unused devices to study staff.
8. A member of the study staff will ensure that all study devices are accounted for, i.e., that the number of unused devices returned is reconciled with reported ring use.
9. The participant will then be asked if she would like to participate in an open-label extension where she can use VR101 for 2 weeks (two devices, 1 week per device). Each participant will be instructed to discontinue use her final VR101 device at day 42 ± 2 and told she will receive a final follow-up call on day 49 ± 2.
10. If the participant would like to continue, a member of the study staff will provide her with two VR101 devices. Participants will be again shown to a private clinic area or restroom to remove her device and (if she has elected to continue) self-

J3 Bioscience, Inc.	Clinical Investigation Plan and Protocol CI03	CI03-CIP Rev. 02 Page 34 of 60
	A Clinical Investigation to Evaluate Efficacy of the J3 Bioscience Lubricating Intravaginal Ring VR101 as a Personal Lubricant Device in Women	

insert one of the devices from the package. Participants will be asked to insert one of these rings per the instructions for use and without clinician input. However, the participant may elect to take the rings with her and insert later at her convenience. The participant should dispose of her used ring in the restroom wastebasket, used rings are not intended to be collected by study staff.

Early Termination Visit

1. If a participant withdraws consent during the study (before Day 26, attempt to schedule a Visit for the participant to return study products and disclose any Adverse Events or concomitant therapy changes. Refer to Section 13 for further detail on classification of AEs and adverse device effects (ADEs).
2. During this Visit, if appropriate, participants will be asked to provide a urine sample for a pregnancy test.
3. If consent has not been withdrawn prior to the Study Visit, participants will be administered the FSFI study, Intercourse / Lubricant Use Study, and queried as needed to complete the Ring Use survey (in that order).
4. The participant will be queried regarding the reason for her withdrawal and the response will be recorded on the Early Termination CRF, record as much detail as possible (e.g. lack of lubrication, too much lubrication, difficulty place/remove a ring, adverse event (related or unrelated to device), etc.)

5.4.4 Interim Follow-Up Call Schedule

Each participant will be contacted by phone on days 7, 14, and 21 to assess their medical condition and to complete the Intercourse / Lubricant Use Survey. Participants will also be reminded to remove their current ring and replace with a fresh ring if they have not already done so. The study staff member administering the call will also query the participant to determine the date and time all ring exchanges (scheduled and un-scheduled) and temporary removals re-insertions, and if any assistance was required for insertion/removal for any of these exchanges/temporary removals.

5.4.5 Terminal Follow-Up Procedure

One (1) week after the last ring is removed, each participant will be contacted to assess her medical condition and to complete a brief questionnaire. Each participant will also be reminded that she may contact the clinic at any time after the study if she is experiencing any discomfort that she believes may be related, directly or indirectly, with use of the ring. If the participant participated in the two-week open-label extension, study staff will query the participant to complete the ring use log (see Section 5.4.8). If a participant is terminated early and returns to the clinic for a final visit (see above), all information and rings can be collected during this visit and an additional follow-up call is not needed.

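### Section 5.4.5 drops the one-week post-removal safety call for any woman who attends an Early Termination visit, however recently her ring came out, and conflicts with the Table 7 footnote

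*Protocol*

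**What the plan says.** The general rule in Protocol Section 5.4.5 is: "One (1) week after the last ring is removed, each participant will be contacted to assess her medical condition". The same contact carries a reminder about self-report: "Each participant will also be reminded that she may contact the clinic at any time after the study". The section then makes an exception for a participant who is terminated early and returns to the clinic: "all information and rings can be collected during this visit and an additional follow-up call is not needed".

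The other places that bear on this are:

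- **Table 7 (Section 5.4.3).** Adverse events are marked at the Early Termination visit and at the final phone call. For a participant who does not elect the extension, "the follow-up will occur on day 35±2 instead of day 49±2". The footnote to the Early Termination column reads "Only if a participant decides to withdraw participation before reaching Day 26".
- **Early Termination visit, Section 5.4.3.** Step 1 tells staff to "attempt to schedule a Visit for the participant to return study products and disclose any Adverse Events". Steps 1 to 4 schedule no later contact.
- **Section 5.3.6.** Women who withdraw or are removed "due to an Adverse Event will be followed as described in Section 13.10". Section 13.10 follows participants who already have a device-related event until it resolves, stabilizes or becomes chronic.
- **Section 13.7.2.** Adverse-event collection runs from consent to the final visit.
- **SAP Section 1.6.** The final safety call is described only for women who complete Visit 2 and go on to the extension.

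**The concern.** The reason given for the waiver does not match the purpose of the call. The call records the woman's condition a week after removal. A visit on the day the ring comes out can collect logs and rings, but it cannot show what happens in the following week. Completers are treated differently: a woman who declines the extension also has her ring-use information completed at Visit 2, yet she is still called.

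Safety capture is what is at stake. Section 2.1 says CI03 will continue the monitoring of VR101 safety. Women who stop early are a group in whom device problems are plausible: step 4 of the Early Termination visit names ring difficulty and adverse events among its example reasons. For them, an event that starts after the visit has no scheduled contact at which anyone would ask about it.

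**Working it through.** **Scale.** SAP Table 1 gives 4 early terminations at Site A and 5 at Site B among 89 and 86 treated women.

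- 4 + 5 = 9, and 9/175 = 5.1%, which agrees with the table.
- By site: 4/89 = 4.5% and 5/86 = 5.8%.
- The table notes that final FSFI lubrication scores exist for all 9. Section 5.4.6 ties the FSFI to visits, so each woman appears to have attended one and to fall under the waiver.

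**Time off-ring at the last scheduled safety question.** Assume the last randomized ring comes out at the visit.

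- Completer who declines the extension: Visit 2 is day 28 ± 2 (26 to 30) and the call is day 35 ± 2 (33 to 37). Nominal interval 35 − 28 = 7 days; shortest 33 − 30 = 3; longest 37 − 26 = 11.
- Early terminator under Section 5.4.5: 0 days if the ring comes out at the visit, more if she removed it earlier. The documents do not give this interval.

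**Does the Table 7 footnote close the gap?** Read literally, it covers any woman not entering the extension, which includes early terminators. Two things count against relying on it.

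- Section 5.4.5 addresses early terminators by name and says the call is not needed. The specific sentence governs.
- The footnote's date is fixed to the calendar, not to removal. For removal on day r, a day 35 ± 2 call falls 33 − r to 37 − r days later. With r = 10 (illustrative) that is 23 to 27 days; with r = 25 it is 8 to 12 days. It approximates one week only for late removals.

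**Does another section supply the contact?** Sections 5.3.6 and 13.10 follow events already known and do not look for new ones. The Early Termination steps add nothing later. Section 13.7.2 stops collection at the final visit, and Section 5.4.5 itself describes the Early Termination visit as a final visit.

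**Would a reinstated call fit?** With a call at 7 ± 2 days after removal, the latest call day is r + 9. For r = 25 that is day 34. The 49-day limit in Section 5.3.4 holds while r + 9 ≤ 49, that is, r ≤ 40. A visit at least 7 − 2 = 5 days after removal already falls at or beyond the start of that call window, so it can stand in for the call.

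**The case against.** The strongest reply is that ending contact at an exit visit is a defensible choice for this device. Section 2.1 records agreement with FDA that safety had been demonstrated, and Section 13.8 calls the device non-significant risk. Self-report routes exist outside the waived call: the instructions for use in Appendix B give a study-coordinator contact for questions or concerns, and the pouch label sends a woman with persisting symptoms to her clinician. Symptomatic women may also have removed the ring before the visit, since the label tells them to stop use on irritation, so 0 days is a worst case. Finally, the plan aims to collect outcomes before consent is withdrawn, so some or all of the 9 women might not have been callable.

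Most of this stands, and it limits the weight of the point. It does not supply a scheduled question, because self-report depends on the woman making the link and calling.

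A reader might infer more than the documents support:

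- **That device-related events, infections in particular, are being missed after removal.** The documents do not show this. The hazard assessment in Appendix C reports no infections in CI01 over a period that included a week after use, and the one CI02 infection it describes resolved when the ring was removed.
- **That early terminators are abandoned or may not be called.** Saying that a call is not needed leaves a site free to make one, and known events are followed under Section 13.10.

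**Conclusion.** The point holds as a minor gap in safety capture. The protocol states a rule that removes a scheduled contact from early terminators who attend a visit, regardless of time off-ring, and the rule conflicts with the literal wording of the Table 7 footnote. The difference is as little as 0 days off-ring against about 7 (3 to 11) for a completer who declines the extension, and it concerns 9 of 175 treated women (5.1%).

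This rests on three assumptions: that the specific sentence in Section 5.4.5 overrides the general footnote; that the final FSFI scores for all 9 mean all 9 attended a visit; and, for the 0-day figure, that the ring came out at that visit. The number who could have benefited is 0 to 9, because the documents do not say how many withdrew consent afterwards; women already followed under Section 13.10 would gain less.

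The primary efficacy analysis is untouched. SAP Sections 10.1 and 10.2 record that follow-up calls and data collection are finished, so the change matters mainly if the plan is reused.

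**What to change.** Make three wording edits, all cheap improvements:

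1. **Section 5.4.5.** Replace the closing clause that drops the call with: *An early terminator who has not withdrawn consent is called 7 ± 2 days after her last ring removal; if her Early Termination visit falls at least 5 days after that removal, the visit serves as this contact.*
2. **Table 7 footnote.** Limit the day 35 ± 2 call to women who complete Visit 2 and decline the extension, and refer early terminators to Section 5.4.5. Otherwise two call dates would remain.
3. **Section 13.7.2.** Let adverse-event collection run to the later of the final visit and the final follow-up call. Otherwise an event first reported on the reinstated call could fall outside the collection window. This also fits Table 7, which already marks adverse events at the final call.

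The cost is these edits, the IRB approval required by Section 10, and 0 to 9 short calls at the early-termination count seen in CI03. No separate edit is needed for the self-report reminder, since the instructions for use already carry the coordinator contact.
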